4.4.1.2.2 Intensity

Intensity for unsolicited non-serious AE will be derived according to the following classification: None, Grade 1, Grade 2, Grade 3, or Missing.

If the unsolicited AE is measurable and its preferred term (PT) is part of the list of solicited reactions, then the measurement is derived based upon and following the same rule than the intensity scales defined in the protocol for that measurable injection site or systemic reaction.

Intensity for the other unsolicited non-serious AEs will correspond to the value reported in the CRB.

The maximum intensity corresponds to the highest intensity for a unique term.

4.4.1.2.3 Last Vaccination

The last vaccination before an unsolicited non-serious AE is derived from the visit numbers provided in the clinical database and is calculated as follows:

- If an unsolicited non-serious AE has a non-missing visit number, the visit number should be used to determine the last vaccination before the unsolicited non-serious AE
- If the visit number is missing, then the start date should be used to determine the last vaccination before the unsolicited non-serious AE

4.4.1.2.4 Time of Onset

Time of onset is derived from the start date of the unsolicited non-serious AE provided in the clinical database and the date of last vaccination:

- start date of the unsolicited non-serious AE – date of previous vaccination

The time of onset should be considered as missing only if one or both of the dates are missing or partially missing.

The unsolicited non-serious AEs will be analyzed “Within 28 days”, which corresponds to AEs with a time of onset between 0 and 28 days after vaccination or missing. An AE with missing time of onset will be considered to have occurred just after the vaccination indicated by the visit number, so will be included in these tables.

Note: Unsolicited non-serious AE that occurred before the 1st vaccination (negative time of onset) or with a time of onset higher than 28 days will not be included in analysis and will be listed separately.

Time of onset will be categorized into and displayed as D0-D3, D4-D7, D8-D14, \geq D15, and Missing.

4.4.1.2.5 Duration

Duration will be derived from the start and end dates of the unsolicited non-serious AE provided in the clinical database:

- end date of unsolicited non-serious AE - start date of unsolicited non-serious AE + 1.

The duration will be considered as missing only if one or both of the start and end dates of the unsolicited non-serious AE was missing or partially missing.

Duration will be categorized and displayed as 1-3 days, 4-7 days, 8-14 days, \geq 15 days, and Missing.

4.4.1.3 SAEs

AESIs will be collected from inclusion until the end of the study as SAEs. AESIs are to be reported and analyzed as SAEs.

4.4.1.3.1 Last Vaccination

The last vaccination before an SAE is derived from the last visit numbers provided in the clinical database and is calculated as follows:

- If an SAE has a non-missing visit number, the visit number should be used to determine the last vaccination before the SAE
- If the visit number is missing, then the start date should be used to determine the last vaccination before the SAE

4.4.1.3.2 Time of Onset

Time of onset will be computed using the same methodology as for unsolicited non-serious AEs described in [Section 4.4.1.2.4](#).

SAEs will be analyzed throughout the study using the following periods:

- Within 28 days after each and any injection
- Within 180 days from 28 days after the last injection
- During the study (ie, all SAEs occurred during the study)

An SAE with missing time of onset will be considered to have occurred just after the vaccination, indicated by the visit number, and will be included in these tables.

Note: SAEs that occurred before the 1st vaccination (ie, negative time of onset or with a time of onset higher than defined 28 days) will not be included in analysis but may be listed separately.

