Epinephrine injection (1:1000) and other appropriate agents used for the control of immediate allergic reactions must be available to treat unexpected reactions (eg, anaphylaxis).

As with all injectable vaccines, appropriate medical treatment and supervision should always be readily available in case of an anaphylactic event following the administration of the vaccine.

Cases of demyelinating disorders (eg, incident multiple sclerosis in adults, acute disseminated encephalomyelitis, transverse myelitis), have been reported following influenza vaccines,

although the National Academy of Medicine (formerly, Institute of Medicine) concluded that the evidence is inadequate to accept or reject a causal relationship (20).

In a study of the 2010–2011 influenza season, the CDC found that there was a risk of fever-associated seizure (convulsion) occurring on the day of influenza vaccination and for 1 day after vaccination in children 6 months through 4 years of age. The risk was higher among children who received concomitant inactivated influenza vaccine and 13-valent pneumococcal conjugate vaccine and peaked at approximately age 16 months. The magnitude of the increased risk was less than 1 episode per 1000 immunized children. A similar risk was found during the 2011–2012 season (in which the formulation of the influenza vaccine used was the same as that used during the 2010–2011 season); however, an increased risk for febrile seizures following influenza vaccination was not observed during the 2012–2013 influenza season. No increased risk was found for children older than 4 years of age. After taking into consideration the benefits and risks of vaccination, no policy change was recommended for use of inactivated influenza vaccine or 13-valent pneumococcal conjugate vaccine (21).

The potential risks listed here are not exhaustive; refer to the US package insert (Fluarix® Quadrivalent) or investigator brochure of the marketed vaccines for additional information regarding potential risks (22) (23).

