- To compare the HAI immune response of QIV-HD to QIV-SD in subjects 6 months through 35 months of age
- To describe the HAI immune response induced by each vaccine against the 4 vaccine strains and according to the different strain formulations used in each of the study influenza seasons
- To describe the SN immune response induced by QIV-HD or QIV-SD against the 4 QIV-HD vaccine strains in a randomized subset of subjects
- To describe the anti-neuraminidase (NA) immune response induced by QIV-HD or QIV-SD in a randomized subset of subjects

Re-vaccination Response

To describe the immune response (HAI method) to vaccination in Season 3 (NH) among subjects re-enrolled from Season 1 (NH) to Season 3 (NH), according to the vaccines received in both Season 1 (NH) and Season 3 (NH)

Safety

- To describe the safety profile (injection site reactions and systemic events) of each vaccine during the 28 days following each vaccination for the ESafAS (all subjects from Sentinel Safety Cohort, all subjects from Season 1, and a subset of subjects from Seasons 2 and 3)
- To describe all SAEs (including AESIs) up to at least 180 days after the last vaccination in all subjects

The endpoints for the secondary objectives are presented in [Section 9.3](#)

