5.2.5 Exclusion Criteria

An individual fulfilling *any* of the following criteria is to be excluded from study enrollment:

- 1) Participation at the time of study enrollment (or in the 4 weeks preceding the first study vaccination) or planned participation during the present study period in another clinical study investigating a vaccine, drug, medical device, or medical procedure.
- 2) For all subjects: Receipt of any vaccine in the 30 days preceding the first study vaccination. For subjects in Immunogenicity Subset: Planned receipt of any vaccine before Visit 2 for subjects receiving 1 dose of influenza vaccine or Visit 3 for subjects receiving 2 doses of influenza vaccine.
- 3) Previous vaccination against influenza in the preceding 6 months with either the study vaccine or another influenza vaccine
- 4) Receipt of immune globulins, blood or blood-derived products in the past 3 months.
- 5) Known or suspected congenital or acquired immunodeficiency (eg, HIV); or receipt of immunosuppressive therapy, such as anti-cancer chemotherapy or radiation therapy, within the preceding 6 months; or long-term systemic corticosteroid therapy (prednisone or equivalent for more than 2 consecutive weeks within the past 3 months).

^a “6 to 35 months” means from the 6th month after birth to the day before the 36th month after birth.

- 6) Known systemic hypersensitivity to any of the vaccine components, or history of a life-threatening reaction to the vaccines used in the study or to a vaccine containing any of the same substances^a. Exception: subjects with an egg allergy are allowed to enroll in the study.
- 7) Thrombocytopenia, bleeding disorder, or receipt of anticoagulants that based on Investigator's judgment contraindicate intramuscular vaccination
- 8) Chronic illness that, in the opinion of the Investigator, is at a stage where it might interfere with study conduct or completion^b.
- 9) Moderate or severe acute illness/infection (according to investigator judgment) on the day of vaccination or febrile illness (temperature $\geq 38.0^{\circ}\text{C}$ [$\geq 100.4^{\circ}\text{F}$]). A prospective subject should not be included in the study until the condition has resolved or the febrile event has subsided.

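### The SAE/AESI periods in SAP 4.4.1.3.2 include no day 0–1 window for convulsions, and the late period, read literally, ends at day 208, after the final call for some children

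*SAP*

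**What the plan says.** Protocol 9.3.3.3.4 lists convulsions among the AESIs and captures them as SAEs; 9.3.3.3.3 makes every febrile convulsion an SAE. SAP 4.4.1.3 adds: "AESIs are to be reported and analyzed as SAEs".

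SAP 4.4.1.3.2 then sets three periods. The first is "Within 28 days after each and any injection", where 28 days has the meaning given in SAP 4.4.1.2.4: "which corresponds to AEs with a time of onset between 0 and 28 days after vaccination or missing". The second is "Within 180 days from 28 days after the last injection". The third takes in every SAE of the study. The second is used again in the subgroup safety tables of SAP 5.1.4.3.

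Protocol 1.3.2 reports, from a study of the 2010–2011 season, a "risk of fever-associated seizure (convulsion) occurring on the day of influenza vaccination and for 1 day after vaccination". The affected ages, 6 months through 4 years, include the whole range of this trial. The excess was below 1 per 1000 immunised children, and "The risk was higher among children who received concomitant inactivated influenza vaccine and 13-valent pneumococcal conjugate vaccine".

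The safety objective in protocol 2.2 is "To describe all SAEs (including AESIs) up to at least 180 days after the last vaccination in all subjects". SAEs are collected from day 0 to the 6-month call or the end of season surveillance (protocol 9.3.3.3.3). For the main cohort that call comes 180 (+14) days after the last dose, or at season end if later (protocol 5.1.4.2 to 5.1.4.5). For sentinel children it comes at 180 (+14) days with no season extension (protocol 5.1.4.1).

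**The concern.** Fever-associated seizure is a vaccine risk for which the protocol gives both a time window and a size. No period set for SAEs or AESIs matches that window. The shortest mixes two risk days with 27 further days of background seizures, so a difference between the vaccine groups confined to day 0 and day 1 would be estimated less precisely than the collected onset dates allow. Outside the ESafAS in Seasons 2 and 3, solicited reactions and unsolicited AEs are not collected (protocol 5.1.3), so the SAE/AESI tables carry most of the early safety information there.

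The late period raises a second, smaller problem. If it runs for 180 days starting 28 days after the last injection, it extends past the last scheduled contact for some children. A table giving percentages of subjects would then treat unobserved days as event-free.

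**Working it through.** **Day arithmetic.** The plan's own figure reproduces: Table of Study Procedures 4 puts the two-dose final call at D208, which is V02 at D28 plus 180 days. That 208 counts from the *first* dose. The late SAE period counts from the *last* injection and ends at 28 + 180 = 208 days after it.

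- Final call: day 180 nominal, day 194 at the end of its window.
- Overshoot on that schedule: 208 − 180 = 28 days, or 208 − 194 = 14 days.
- Season-end rule: surveillance reaches day 208 only if the last injection falls on or before 30 April 2023 − 208 days = 4 October 2022 (Season 1), 31 October 2023 − 208 days = 6 April 2023 (Season 2), or 30 April 2024 − 208 days = 5 October 2023 (Season 3).
- For later last doses the shortfall grows. After a last dose on 15 October 2022, season end is day 197, so 208 − 197 = 11 days are missing at the nominal call. The full 28 days at the nominal call is reached for last doses from about 1–2 November (NH) or 4 May (SH), where season end no longer falls after day 180.
- Sentinel children have no season extension and are always 14–28 days short.

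**Background time.** Days 0 to 28 are 29 days; D0–D1 is 2 days. The ratio is 29/2 = 14.5 (28/2 = 14 if day 0 is not counted). If the D0–D3 category of SAP 4.4.1.2.4 were used, it would be 4/2 = 2. With a constant background, a relative risk RR on D0–D1 appears in a window k times as long as 1 + (RR − 1)/k: RR 10 becomes 1 + 9/14.5 = 1.62 over D0–D28 and 1 + 9/2 = 5.5 over D0–D3. The excess count does not change: 6,610 × 1/1000 = 6.6 cases in any window that contains D0–D1.

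**Precision.** Inputs from the documents: 13,220 randomised 1:1, so 6,610 per arm (SAP 5.5), and an excess of 1 per 1000 children, the upper figure in protocol 1.3.2. Assumed: background of 0.1, 1 or 3 convulsions per 100 child-years, and the whole excess falling in the QIV-HD group.

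Expected QIV-SD count = 6,610 × rate × days/365; for example 6,610 × 0.01 × 29/365 = 5.3. QIV-HD adds 6.6. Power is for the exact binomial test of the QIV-HD share conditional on the total, one-sided 2.5%, with Poisson totals. The 95% CI half-width of the risk difference is approximately 1.96 × √(sum of the two expected counts)/6,610.

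| Background per 100 child-years | Expected SD / HD, D0–D1 | Expected SD / HD, D0–D28 | Power D0–D1 | Power D0–D28 | Half-width per 1000, D0–D1 | Half-width per 1000, D0–D28 |
|---|---|---|---|---|---|---|
| 0.1 | 0.04 / 6.65 | 0.5 / 7.1 | 64% | 57% | 0.77 | 0.82 |
| 1 | 0.4 / 7.0 | 5.3 / 11.9 | 59% | 28% | 0.80 | 1.23 |
| 3 | 1.1 / 7.7 | 15.8 / 22.4 | 50% | 15% | 0.88 | 1.83 |

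On the same inputs D0–D3 gives 55% and 41% at backgrounds of 1 and 3. With an excess of 0.5 per 1000, the 1–3 range gives 12–13% on D0–D1 against 6–9% over D0–D28.

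**The case against.** SAE analysis here is descriptive: no hypothesis is tested, so no stated error rate or sample size changes. Onset dates are recorded for every SAE, so a D0–D1 count could be produced at any time. The IDMC sees unblinded Season 1 safety data under a separate interim SAP (SAP 5.4.2), which is not available and might contain such a table. All of this stands, and it limits the point to what is pre-specified in the SAP.

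SAP 4.4.1.3.2 also refers to the onset method of 4.4.1.2.4, where D0–D3 is a display category. But the reference concerns how onset is computed. The section then sets its own SAE periods and does not say that the display categories carry over.

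The power inputs favour the concern. The protocol's figure is an upper bound after ordinary inactivated influenza vaccine, and QIV-SD is one too, so nothing in the documents supports giving the whole excess to QIV-HD. The same section reports no increased risk in 2012–2013. Children with a history of seizure disorder are excluded, which bears on the background rate. The power figures are therefore illustrations.

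On the late period, both arms share the same schedule, so the shortfall gives no reason to expect bias between them. The wording may have been meant as day 28 to day 180.

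**Conclusion.** Two limited defects stand. First, no SAE/AESI period is shorter than 28 days, although the protocol names a two-day convulsion window within the trial's age range. The cost is precision, and its size depends on the background: power falls from 50–59% to 15–28% at an assumed 1–3 per 100 child-years, but only from 64% to 57% at 0.1, all for 1 per 1000 in QIV-HD alone. Second, the late period ends at day 208. That is 14–28 days beyond a call on the 180 (+14) schedule, and affects sentinel children and main-cohort children last vaccinated after about 4–5 October (NH) or 6 April (SH), by less where season end falls between day 180 and day 208.

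A reader might infer more, which the documents do not support:

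- That a convulsion signal is diluted 14-fold. The 14 is a ratio of background time; the excess count and risk difference stay whole.
- That the comparison could not show such an excess. It would show it less precisely.
- That no period fits SAE collection. The whole-study period does.
- That the late period outruns follow-up for everyone. Earlier-vaccinated main-cohort children are followed to day 208 or beyond.

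**What to change.** In SAP 4.4.1.3.2 and 5.1.4.3:

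1. Add a descriptive table of convulsion AESIs, and of febrile convulsion alone, with onset on D0–D1 after each and any injection, by vaccine group with rate difference and 95% CI. Keep the 28-day table. Show missing onset on its own row, because the SAP's rule places such events just after vaccination and would otherwise put them in D0–D1.
2. Define the late period as day 29 through day 180 after the last injection. SAEs collected after day 180 stay in the whole-study period, so none is lost.

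A co-vaccination breakdown is optional. Other planned vaccines are barred only for one group ("For subjects in Immunogenicity Subset: Planned receipt of any vaccine before Visit 2", or Visit 3 for two-dose children), so children outside it may receive another vaccine on day 0, and all vaccines are recorded and coded (protocol 6.6). Any such split should cover only vaccines given on the day of study vaccination and be labelled descriptive. A vaccine given on day 1 can follow a day 0 convulsion, or be withheld because of one.

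The cost is SAP wording and one or two extra tables from data already collected. Their counts will be small.

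### The SAE onset note in SAP 4.4.1.3.2 treats onset later than 28 days as a kind of pre-vaccination event and excludes it; the clause should be deleted.

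*SAP*

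**What the plan says.** SAP 4.4.1.3.2 borrows its onset rule: "Time of onset will be computed using the same methodology as for unsolicited non-serious AEs described in" SAP 4.4.1.2.4. There, onset is derived from the "start date of the unsolicited non-serious AE provided in the clinical database and the date of last vaccination", as the first date minus the second.

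The section then states that "SAEs will be analyzed throughout the study using the following periods", and lists three:

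1. within 28 days after each and any injection;
2. "Within 180 days from 28 days after the last injection";
3. "During the study (ie, all SAEs occurred during the study").

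An SAE with missing onset is placed just after the vaccination shown by its visit number and stays in the tables.

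The closing note takes SAEs from before the first vaccination as its subject and explains that phrase in a bracket. The bracket and what follows it read: "negative time of onset or with a time of onset higher than defined 28 days) will not be included in analysis". Listing such events separately is left optional.

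The matching note for non-serious AEs in SAP 4.4.1.2.4 is built differently. Its wording for the excluded events is: "occurred before the 1st vaccination (negative time of onset) or with a time of onset higher than 28 days will not be included in analysis". There the bracket closes after the negative onset, and the 28-day limit is a second, separate exclusion.

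**The concern.** The note explains a pre-vaccination SAE in two ways, and the second is impossible under the SAP's own definition of onset. The sentence sits in a derivation section, where a programmer looks for inclusion rules. If the bracket is coded as it stands, any SAE with known onset more than 28 days after the previous dose leaves the analysis.

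The summaries at stake are the late-period and whole-study SAE tables. SAP 4.4.1.3 has AESIs analysed as SAEs, so late AESIs such as Guillain-Barré syndrome or convulsions would leave those tables as well. Data collection, expedited reporting, efficacy analyses and hypothesis tests are not affected.

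**Working it through.** The plan gives no figure on this point, so the check is one of consistency, followed by a count of days.

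**Can the clause describe a pre-vaccination SAE?** Onset = SAE start date − date of the previous vaccination (SAP 4.4.1.2.4, applied to SAEs by 4.4.1.3.2). An event before the first dose gives a negative value. A value above 28 requires a dose at least 29 days earlier. The two halves of the bracket cannot describe the same class of event.

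**Does it fit as a second exclusion?** Compare it with the rest of the plan:

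| Place | SAEs to be summarised | Effect of removing onset > 28 days |
|---|---|---|
| SAP 4.4.1.3.2, period 1 | Within 28 days of each and any injection | None |
| SAP 4.4.1.3.2, period 2 | Starting 28 days after the last injection | Removes what the period exists to count |
| SAP 4.4.1.3.2, period 3 | All SAEs during the study | Cut to SAEs within 28 days of a dose |
| SAP 5.1.4.3 | Late-period SAEs and AESIs by subgroup | As period 2 |
| SAP 2.2 and Protocol 2.2 | All SAEs and AESIs to at least 180 days after the last vaccination | Conflict |
| Protocol 9.3.3.1 | SAEs and AESIs throughout the study | Conflict |

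So the clause conflicts with 2 of the 3 listed periods. It also gives an odd result for missing data: an SAE with no usable date is counted, while one with a known late date is not.

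**How much follow-up does it reach?** Inputs, from the Tables of Study Procedures for the main cohort: one dose at D0 with follow-up to at least D180; or doses at D0 and D28 with follow-up to at least D208. Days are counted inclusively, and onset is measured from the previous dose.

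- One dose: D0 to D180 is 181 days. Onset > 28 covers D29 to D180, which is 180 − 28 = 152 days. 152 / 181 = 84.0%.
- Two doses: D0 to D208 is 209 days. Onset > 28 after dose 2 covers D57 to D208, which is 208 − 56 = 152 days. 152 / 209 = 72.7%.
- Period 2, taken to begin on day 29 after the last injection: if it ends on day 28 + 180 = 208 it has 180 days, and if it ends on day 180 it has 152. On either reading the clause leaves 0 days.

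**After deletion:** 0 of 181 and 0 of 209 post-vaccination days are excluded, and only negative onset remains out. Period 1 needs no help from the note, because its own definition stops at 28 days.

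**Can follow-up pass day 208?** The closing call falls at 180 (+14) days, so up to 180 + 14 = 194 days after the last dose, unless the season ends later. With the protocol's season dates, 4 October 2022 + 208 days = 30 April 2023 and 6 April 2023 + 208 days = 31 October 2023. A child whose last dose precedes those dates could therefore be followed beyond day 208. Enrolment dates are not stated, so this is conditional. It matters only for the wording of the optional sentence in the fix.

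**The case against.** The best defence is grammatical. The subject of the note is SAEs before the first vaccination, and the bracket opens with ie, so it explains that subject and adds no second class. Read strictly, the impossible half selects nothing and no SAE is lost. Late SAEs drop out only if a programmer treats the bracket as a free-standing rule.

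The intent is also plain. The lead sentence and third period of the same section, SAP 5.1.4.3, and the objectives and endpoint all call for late SAEs. A late-period table with no dated events would be noticed at output review.

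The second argument stands and is why the point is minor. The first does not rescue the text: on one reading the clause is empty, on the other it contradicts the plan, and on neither does it do useful work. The option to list the events elsewhere is no remedy, because the listing is optional and lies outside the analysis.

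It is also fair to say that the percentages above are shares of follow-up days under the free-standing reading. They say nothing about the share of SAEs and should not be used to raise the weight of the point. Finally, the late period can be read as ending on day 180 or day 208; the defect and its cure are the same on both.

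**Conclusion.** The concern holds, as a minor error in one stated inclusion rule, with high confidence. The contradiction is visible within SAP 4.4.1.3.2 once the onset definition in 4.4.1.2.4 is applied. There is no real doubt about which SAEs are meant to be analysed.

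The size is a matter of scope: two of three SAE periods, and 152 days of minimum follow-up per child if the clause is applied. The day counts assume the planned schedule and minimum follow-up; longer seasonal follow-up would raise them. No share of events is claimed.

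That the words were carried over from the note on non-serious AEs is an inference from the near-identical wording. The conclusion does not depend on it.

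**What to change.** In the closing note of SAP 4.4.1.3.2, delete the part of the bracket about onset higher than 28 days and close the bracket after negative time of onset. The note then covers only SAEs that precede the first vaccination, which stay out of the analysis and may be listed.

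If a clarifying sentence is wanted, it could say: *an SAE with onset more than 28 days after an injection counts in every SAE table whose defined period covers that onset, and every SAE with onset on or after the first vaccination counts in the during-the-study table.* On this wording an SAE beginning more than 208 days after the last injection appears only in the whole-study table, whichever way the end of the late period is read.

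The late-period definition need not change for this correction, though the same edit is a convenient place to state whether it ends on day 180 or day 208. The cost is one deleted clause and one optional sentence. No new data are needed, and the planned tables and periods stay as they are.
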